7. PLANNED ANALYSIS

The format of the listings and tables will follow the BI guideline "Reporting of clinical trials and project summaries" [\(6\)](#).

The individual values of all subjects will be listed. Listings will be sorted by treatment or sequence group, subject number and visit (if visit is applicable in the respective listing). AE listings will be sorted by assigned treatment (see [Section 7.8.1](#) below for details). The listings will be contained in Appendix 16.2 (SDL) of the CTR.

The following standard descriptive statistical parameters will be displayed in summary tables of continuous variables:

N	number of non-missing observations
Mean	arithmetic mean
SD	standard deviation
Min	minimum
Median	median
Max	maximum

For plasma concentrations as well as for all PK parameters the following descriptive statistics will additionally be calculated:

CV	arithmetic coefficient of variation
gMean	geometric mean
gCV	geometric coefficient of variation

For PK parameters the following descriptive statistics will additionally be calculated:

P10	10 th percentile
Q1	1 st quartile
Q3	3 rd quartile
P90	90 th percentile

The data format for descriptive statistics of plasma concentrations will be identical with the data format of the respective concentrations. The descriptive statistics of PK parameters will be calculated using the individual values with the number of decimal places as provided by the evaluation program. Then the individual values as well as the descriptive statistics will be reported with three significant digits in the CTR.

Tabulations of frequencies for categorical data will include all possible categories and will display the number of observations in a category as well as the percentage (%) relative to the respective treatment group. Percentages will be rounded to one decimal place. The category missing will be displayed if and only if there actually are missing values. Percentages will be based on all subjects in the respective subject set whether they have non-missing values or not.

7.1 DISPOSITION, DEMOGRAPHIC AND OTHER BASELINE CHARACTERISTICS

Only descriptive statistics are planned for this section of the CTR. Whereas disposition will be based on the SCS, demographics and other baseline characteristics will be presented based on the TS.

7.2 CONCOMITANT DISEASES AND MEDICATION

Concomitant diseases will be coded according to the most recent version of MedDRA. Concomitant medication will be coded according to the most recent version of the World Health Organisation – Drug Dictionary. Concomitant non-drug therapies will be coded according to the most recent version of MedDRA.

Only descriptive statistics based on the TS are planned for this section of the CTR.

CTP Section 4.2.2.1: *“In principle, no concomitant therapy is allowed. All concomitant or rescue therapies will be recorded (including time of intake on study days) on the appropriate pages of the CRF.”*

A medication will be considered concomitant to a treatment period, if it

- is ongoing at the time of study drug administration, or
- starts within the analysis phase of the respective treatment (see [Section 6.1](#) for a definition of treatments and analysis phases).

Concomitant medications as well as their time relative to the previous and subsequent study drug administration will be listed.

The relevance of the concomitant therapies to the evaluation of PK will be decided no later than at the RPM.

7.3 TREATMENT COMPLIANCE

Treatment compliance will not be analysed as a specific endpoint. Any deviations from complete intake will be addressed in the Report Planning Meeting (cf. [Section 6.2](#)) and described in the CTR.

7.4 PRIMARY ENDPOINTS

7.4.1 Primary analysis of the primary endpoint

The analysis of the primary endpoint will be based on the PDS.

CTP Section 7.2.2: *“A linear mixed effects model will be used for the analysis of the primary endpoint. This model will include effects for sequence, subject within sequence, period, baseline values (obtained at screening visit 2 prior to and on ketamine) and treatment. The*

effect 'subject within sequence' will be considered as random, whereas the other effects will be considered as fixed. All three periods (if available) will be included in the analysis."

The corresponding baseline values are described in [Section 6.7](#) of this TSAP (see baseline definition for 'On-ketamine analysis of CANTAB, [REDACTED] parameters (according to Section 2.2.2.2 of the CTP)').

The model is described by the following equation:

$$y_{ijklmp} = \mu + \zeta_i + s_{im} + \pi_j + \tau_k + \vartheta_p + \alpha_l + e_{ijklmp}, \text{ where}$$

y_{ijklmp} = response measured on subject m in sequence i receiving treatment k in period j with pre-ketamine baseline p and during-ketamine baseline l

μ = the overall mean,

ζ_i = the i^{th} sequence effect, $i = 1, 2, \dots, 18$

s_{im} = the effect associated with the m^{th} subject in the i^{th} sequence, $m = 1, 2, \dots, n_i$

π_j = the j^{th} period effect, $j = 1, 2, 3$

τ_k = the k^{th} treatment effect, $k = 1, 2, 3, 4$

ϑ_p = the p^{th} pre-ketamine baseline effect, $p = 1, \dots, 40$

α_l = the l^{th} during-ketamine baseline effect, $l = 1, \dots, 40$

e_{ijklmp} = the random error associated with subject m in sequence i who received treatment k in period j with pre-ketamine baseline p and during-ketamine baseline l

where $s_{im} \sim N(0, \sigma_2)$ i.i.d., $e_{ijklmp} \sim N(0, \sigma_2)$ i.i.d. and s_{im} , e_{ijklmp} are independent random variables.

CTP Section 7: *The primary and secondary PD endpoints will be compared between BI 409306 and placebo as well as BI 425809 and placebo. The Lamotrigine (T1) treatment period acts as a positive control group. It is not planned to compare PD effects between Lamotrigine, BI 425809 and BI 409306. The primary and secondary PD endpoints will be compared between Lamotrigine and placebo to investigate the sensitivity of the design.*

In addition the primary endpoint will be analysed descriptively for each study treatment.

N, mean, SD, median, minimum and maximum will be provided for absolute values as well as for the change from baseline. Additionally placebo-corrected values will be presented as difference between the value of the respective study treatment and the value of placebo.

Profile plots will be provided to display absolute pre- and during-ketamine values at baseline as well as for each treatment period.

A large black rectangular redaction box covers the majority of the page content, from approximately y=113 to y=300. It is positioned in the center of the page, with a smaller black square redaction in the top-left corner at approximately x=113, y=113.

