** infusion can be prolonged for a maximum of 15 min, i.e. to 105 min in total, in case of delays from the planned time of the assessments on ketamine, or terminated earlier if the planned assessments on ketamine are completed or any test drops out*

Proprietary confidential information © 2021 Boehringer Ingelheim International GmbH or one or more of its affiliated companies

	
** each subject will receive R treatment and 2 of 3 randomly allocated T1 or T2 or T3; each treatment period is separated by a washout of at least 11 days between study drug administrations

Statistical methods	
The differences between Lamotrigine and Placebo as well as BI 409306 and Placebo, and BI 425809 and Placebo will be evaluated for the primary endpoint based on a linear mixed effects model. The statistical model will include fixed effects for treatment, sequence, period and baseline values (pre and on ketamine at Visit 2), whereas “subject within sequence” will be included as a random effect. Formal hypotheses tests will not be performed, instead the adjusted mean differences and their 95% confidence intervals will be shown.
 
Descriptive statistics will be calculated for all endpoints.

FLOW CHART A (SUMMARY)

[figure not shown]
Period	Visit	Day	Planned time (relative to Drug administration (I)) [h:min]	Event and comment	Safety laboratory ²⁶	Targeted physical examination ²⁹	DSST, MOAA/S, CADSS, SFST ³⁰	C-SSRS ³¹	CANTAB (RVP, SWM, PAL) ^{8,19}	12-lead ECG ³²	Continuous ECG monitoring ³²	Vital signs (BP, PR, SaO ₂) ²⁴	AEs and concomitant therapy ³³
			Approximate clock time of actual day [hh:min]										
Screening ⁶	1/2/3	3/4/5	-28 to -9	Screening Examination ¹	x ¹					x ¹			
				Admission to trial site ⁹ for Screening Ketamine Challenge ²	x ⁷							x ¹	
			-22 to -3	-12:00 20:00 ⁵									x
				-2:00 06:00 ²		x ²						x ²	x ²
				-0:30 07:30	Light breakfast ¹⁰								
				0:00 ⁸ 08:00	240 mL fluid intake								
				2:55 10:55	Light snack (clear liquid) ¹⁰								
				3:00 11:00	240 mL fluid intake								
				3:25 11:25									
				3:36 11:36									
				4:20 12:20	CANTAB ¹⁹ ,								
				4:55 12:55							x	x ¹⁴	x
				5:00 13:00	Start of ketamine infusion ¹¹								
				5:06 13:06	CANTAB ¹⁹ ,								x
				5:26 13:26									
				5:40 13:40									x
				6:00 14:00									
				6:20 14:20									x
				6:30 14:30	Stop of ketamine infusion ¹²								
				7:00 15:00							x		x

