3.3.5 Replacement of subjects

In case some subjects do not complete the trial, the Clinical Trial Lead together with the Trial Statistician are to decide, if and how many subjects will be replaced. A replacement subject will be assigned a unique trial subject number, and will be assigned to the same treatment as the subject he replaces.

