7.2.2 Primary endpoint analyses

A linear mixed effects model will be used for the analysis of the primary endpoint. This model will include effects for sequence, subject within sequence, period, baseline values (obtained at screening visit 2 prior to and on ketamine) and treatment. The effect 'subject within sequence' will be considered as random, whereas the other effects will be considered as fixed. All three periods (if available) will be included in the analysis.

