So far no experience exist with the trial design in this setting and sequence or period effects cannot be excluded a priori. Therefore the sample size of 36 subjects, i.e. 2 per sequence and at least 8 per period is deemed the minimum to investigate whether such effects potentially exist.

8. INFORMED CONSENT, TRIAL RECORDS, DATA PROTECTION, PUBLICATION POLICY, AND ADMINISTRATIVE STRUCTURE

The trial will be carried out in compliance with the protocol, the ethical principles laid down in the Declaration of Helsinki, in accordance with the ICH Harmonized Guideline for Good Clinical Practice (GCP), relevant BI Standard Operating Procedures (SOPs), the EU regulation 536/2014, and other relevant regulations. Investigators and site staff must adhere to these principles.

Standard medical care (prophylactic, diagnostic, and therapeutic procedures) remains the responsibility of the subject's treating physician.

The investigator will inform the sponsor immediately of any urgent safety measures taken to protect the trial subjects against any immediate hazard, as well as of any serious breaches of the protocol or of ICH GCP.

The Boehringer Ingelheim transparency and publication policy can be found on the following webpage: trials.boehringer-ingelheim.com. The rights of the investigator and of the sponsor with regard to publication of the results of this trial are described in the investigator contract. As a general rule, no trial results should be published prior to archiving of the CTR.

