6.7 BASELINE, TIME WINDOWS AND CALCULATED VISITS

Due to the different analysing approaches with regard to the consideration of ketamine, baselines for pharmacodynamic and safety endpoints are defined separately.

[figure not shown]
On-ketamine analysis of CANTAB, [REDACTED] parameters (according to Section 2.2.2.2 of the CTP):

CTP Section 6.2.1: “*For the Screening Ketamine Challenge eligible subjects will come to the clinic in the morning of the test day, where they will participate in two assessment-sessions:*

- *Screening Baseline (= SCR BL)*
CANTAB tests, [REDACTED] will be done without any treatment, i.e. with no ketamine infusion
- *Screening Ketamine (= SCR KET)*
CANTAB tests, [REDACTED] will be done during ketamine infusion
[...]

The assessments of SCR KET will also be used as baseline for the assessments performed on the test days of the treatment periods, i.e. under treatments T1, T2, T3 and R.”

For the analysis of the pharmacodynamic endpoints (CANTAB tests, [REDACTED] two baselines exist. The pre-ketamine baseline is defined as the last non-missing value prior to start of ketamine infusion at screening. The during-ketamine baseline is defined as the first non-missing value during ketamine infusion at screening.

Safety analyses:

For safety analyses the baseline is defined as the last available value prior to administration of the respective treatment.

For ECG as well as vital signs a separate baseline can be defined for each treatment period as a pre-dose assessment on Day 1 (at Visit 3/4/5) is available.

Time windows are defined in Section 6.1 of the CTP. Adherence to time windows will be checked at the Report Planning Meeting.

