7.5.2.1 Secondary endpoint analysis

[figure not shown]
According to the CTP Section 7.2.3 the secondary endpoints will be assessed statistically using the same methods as described for the primary endpoint (see also Section 7.4.1 of this TSAP).

[figure not shown]
the *Journal of the American Statistical Association* (1973) 68, 352-358. The *Journal of the American Statistical Association* (1973) 68, 352-358.

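### Does the 1-to-40 indexing of the two baselines in the SAP 7.4.1 equation spoil the primary model?

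*SAP*

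**What the plan says.** Protocol 7.2.2 specifies a linear mixed model with subject within sequence as the random term. The fixed terms are sequence, period and "baseline values (obtained at screening visit 2 prior to and on ketamine) and treatment". SAP 7.4.1 repeats that description and then writes the model out. The equation has 18 sequence effects, 3 period effects, 4 treatment effects, a "pre-ketamine baseline effect" with index p = 1 to 40 and a "during-ketamine baseline effect" with index l = 1 to 40. Neither baseline term shows a regression coefficient or a score.

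SAP 6.7 says what the baselines are: "The pre-ketamine baseline is defined as the last non-missing value prior to start of ketamine infusion at screening", and, for the other, the first usable value obtained during the screening infusion. Each subject therefore has one value of each, the same in all three periods.

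The protocol synopsis rules out formal tests and says that "the adjusted mean differences and their 95% confidence intervals will be shown". For SWMBE468 and RVPA, SAP 7.5.2.1 states that "the secondary endpoints will be assessed statistically using the same methods as described for the primary endpoint". Protocol 7.5 defends 36 subjects partly on the ground that "sequence or period effects cannot be excluded a priori". The documents do not explain the figure of 40. Protocol 3.3.5 allows for replacements (the trial lead and statistician "are to decide, if and how many subjects will be replaced"), which may be the reason.

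**The concern.** The equation gives the baselines the same form as sequence, period and treatment: an effect with numbered levels. A programmer who followed it to the letter would declare both baselines as classification factors. Because the baselines do not vary within a subject, these factors compete with sequence and with the random subject effect for the same between-subject degrees of freedom, and there are too few.

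Three things would be at stake. Sequence effects would become largely or wholly non-estimable, although looking for them is part of the case for N = 36. The between-subject variance could usually not be separated from the baseline effects. Adjusted treatment means would usually not be estimable. A second programmer, working from the prose alone, would enter two covariates and fit a different model.

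**Working it through.** **1. The plan's own figure.** Protocol Table 7.5: 1 rests on 24 within-subject comparisons. For a true difference of 4 errors and SD 12, the standard error is 12/√24 = 2.449, and P(observed ≥ 2) = 1 − Φ((2 − 4)/2.449) = 1 − Φ(−0.816) = 79.3%. The table gives 80%, and the other cells agree within rounding. The sample-size reasoning thus uses within-subject differences, to which the baselines contribute nothing.

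**2. Between-subject degrees of freedom.** Inputs: 36 subjects and 18 sequences (Protocol 3.1 and 7.5), one value of each baseline per subject (SAP 6.7).

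- Total: 36 − 1 = 35. After sequence: 35 − 17 = 18.
- Two linear covariates: 18 − 2 = 16 left. With 40 subjects: 39 − 17 − 2 = 20.
- Literal factors, 40 subjects and 40 distinct values: one baseline alone takes 40 − 1 = 39, so nothing is left.

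**3. Literal factors with realistic ties.** The documents give no baseline distribution, so the spreads are assumptions: integer PALTEA28 scores, a ketamine-induced change of at least 10 (the entry criterion), 36 subjects, 400 simulated data sets per row.

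| SD pre-ketamine / SD change | mean distinct values, pre / on | data sets with 0 df left | most df left |
|---|---|---|---|
| 2 / 3 | 8.8 / 13.5 | 40% | 4 |
| 3 / 3 | 12.0 / 15.1 | 76% | 4 |
| 4 / 6 | 14.5 / 20.0 | 94% | 1 |
| 8 / 8 | 18.9 / 23.4 | 96% | 2 |
| 12 / 12 | 19.8 / 25.4 | 91% | 2 |

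In a separate set of four assumed spreads (median 13–22 pre-ketamine and 15.5–25 on-ketamine levels), on average 1.2 to 10.0 of the 17 sequence degrees of freedom stayed estimable, and equal-weight adjusted means never did. For RVPA to four decimals, where almost every subject has his own value, no error df remained in any data set. So the literal model is indeed degenerate between subjects.

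**4. Effect on the planned comparisons, complete data.** Each active appears in 4 sequences per period (8 subjects) and placebo in 6 (12 subjects), so period is balanced against treatment. The pair of actives that a subject receives is fixed by his sequence. With sequence fixed, subject totals therefore carry no treatment information, and everything comes from within subjects.

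For blocks of three, the information on a treatment given to r subjects is r − r/3, and the cross term for two treatments sharing λ subjects is −λ/3. For the actives, r = 24 gives 24 − 8 = 16; two actives share λ = 12 subjects, giving −4. With placebo as reference, the matrix for the three actives is 20I − 4J. Its inverse is (1/20)(I + (4/8)J), with diagonal 1.5/20 = 0.075.

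- Standard error of each active-minus-placebo difference: √0.075 = 0.2739 residual SD.
- Residual degrees of freedom: 108 observations − 36 subjects − 2 periods − 3 treatments = 67.

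No baseline term enters either line. Generalised least squares with subject-to-residual variance ratios of 0.5, 1 and 3 gave 0.2739 and 67 with factors, with covariates and with no baseline at all.

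**5. With dropout (assumed).** With 2, 4 or 8 subjects missing period 3, factor coding raised the standard error by at most 0.6% over covariates. With 6 of 36 dropping out, the average rise was 0.2–0.8%, with a maximum of 3.3%.

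**6. Which reading the text supports.** Protocol 7.2.2 speaks of values, and SAP 7.4.1 repeats this directly above the equation and refers to 6.7, which also defines a value. SAP 7.4.1 then plans changes from baseline, which needs a numeric score. SAP section 4 says that, apart from added summaries and plots, the analyses follow the protocol's methods, so the equation is offered as a restatement of the protocol model. Only the index ranges point the other way.

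**The case for a change.** The best case for a change is this. The equation is the only explicit model in the visible text. The SAP exists to give technical detail, and neither document calls the baselines continuous. The same equation serves RVPA, where literal coding does most damage. Protocol 7.5 names sequence effects as something that 36 subjects should allow the trial to examine. Rewriting the two terms would cost one line.

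Much of this stands. The notation is loose, the degrees-of-freedom arithmetic is right, and a literal fit would remove most of the sequence information at moderate spreads (much less with very narrow scores). It does not lead to a change, for three reasons. First, a literal fit is unlikely: the prose points to numeric scores, and a model with no between-subject error would be hard to overlook when run. Second, sequence effects appear in Protocol 7.5 only as a reason for the sample size; no visible passage specifies a sequence estimate or test. Period effects are kept under either coding. The synopsis promises adjusted differences, not adjusted means, and SAP 7.4.1 adds only descriptive statistics per treatment. Third, SAP 6.1 refers to an ADS Plan for technical implementation, and part of 7.4.1 is redacted. Neither can be seen, and either may already settle the coding.

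**Conclusion.** This is imprecise notation in one equation, which analysts would resolve sensibly from the surrounding text; correcting it would alter no planned result. The three active-minus-placebo differences have a standard error of 0.274 residual SD and 67 residual degrees of freedom with complete data, whether the baselines are factors, covariates or absent. Under the dropout patterns tried, the average cost of the literal coding stays below 1%, with a maximum of 3.3%. The trial is exploratory and tests no hypothesis, so no decision rule turns on the quantities that the literal fit would lose.

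The within-subject result follows from the 18 listed sequences with 2 subjects each and needs no assumption about the scores. The extent of the between-subject loss does depend on assumed baseline spreads. The dropout figures rest on assumed numbers and patterns of missing periods. The judgement would differ if the redacted text or the ADS Plan called for reported sequence effects, subject variance or adjusted means from a factor-coded model; nothing visible suggests that.

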7.5 SECONDARY ENDPOINTS

7.5.1 Key secondary endpoints

This section is not applicable as no key secondary endpoint has been specified in the protocol.

7.5.2 Secondary endpoints

The analysis of the secondary endpoints will be based on the PDS.

7.5.2.1 Secondary endpoint analysis

[figure not shown]
According to the CTP Section 7.2.3 the secondary endpoints will be assessed statistically using the same methods as described for the primary endpoint (see also Section 7.4.1 of this TSAP).

[figure not shown]
the *Journal of the American Statistical Association* (1973) 68, 352-358. The *Journal of the American Statistical Association* (1973) 68, 352-358.

7.6.1 Safety parameters

Safety and tolerability endpoints will be analysed as described in [Section 7.8](#) of this TSAP.

A large, solid black rectangular box covers the majority of the page content, starting below the section header and ending above the page footer.

7.7 EXTENT OF EXPOSURE

Descriptive statistics are planned for this section of the report.

7.8 SAFETY ANALYSIS

All safety analyses for BI 409306, BI 425809, lamotrigine and ketamine will be performed on the TS.

CTP Section 7.2.5: “*The safety analysis will be done by ‘treatment at onset’.*”

7.8.1 Adverse Events

AEs will be coded with the most recent version of MedDRA.

The analyses of AEs will be descriptive in nature. All analyses of AEs will be based on the number of subjects with AEs and not on the number of AEs.

For further details on summarization of AE data, please refer to "Analysis and Presentation of Adverse Event Data from Clinical Trials" [\(7\)](#) and "Handling of missing and incomplete AE dates" [\(3\)](#).

All AEs will be assigned to the screening, on-treatment or follow-up phase as defined in [Section 6.1](#). AEs will be analysed based on treatments as actually received, defined in [Table 6.1: 1](#).

CTP Section 7.2.5: “Statistical analysis and reporting of adverse events will concentrate on treatment-emergent adverse events, i.e. all adverse events occurring between start of treatment and end of the REP. Adverse events that start before first drug intake and deteriorate under treatment will also be considered as ‘treatment-emergent’.”

The longest REP, i.e. 11 days will be taken for all study treatments (Placebo, BI 409306, BI 425809 and Lamotrigine) to avoid any bias which might occur due to different observation times. This may lead to an overestimation of AEs in the treatment periods in which subjects received a study treatment with considerably lower REP.

An overall summary of AEs will be presented. This overall summary will comprise summary statistics for the class of AESIs.

CTP Section 5.2.6.1.4: *The following are considered as AESIs:*

- *Hepatic injury*
A hepatic injury is defined by the following alterations of hepatic laboratory parameters:
 - *An elevation of AST (aspartate transaminase) and/or ALT (alanine transaminase) ≥ 3 fold ULN combined with an elevation of total bilirubin ≥ 2 fold ULN measured in the same blood sample, or*
 - *Aminotransferase (ALT, and/or AST) elevations ≥ 10 fold ULN*

The investigator had to classify on the eCRF whether an observed AE was an AESI or not.

According to ICH E3 (8), in addition to Deaths and Serious Adverse Events, ‘other significant’ AEs need to be listed in the clinical trial report. These will be any non-serious adverse event that led to an action taken with study drug (e.g. discontinuation or dose reduced or interrupted).

The frequency of subjects with AEs will be summarised by treatment, primary SOC and preferred term. AEs will also be summarized by maximum intensity. AEs which were considered by the investigator to be drug related will be presented separately. Separate tables will also be provided for subjects with SAEs, related SAEs and subjects with AESIs.

The SOCs and preferred terms within SOCs will be sorted by descending frequency over all treatment groups.

For disclosure of AE data on ClinicalTrials.gov, the frequency of subjects with non-serious AEs occurring with an incidence of greater than 5 % (in preferred terms) will be summarised by treatment, primary SOC and preferred term. The frequency of subjects with SAEs will also be summarised.

For disclosure of AE data in the EudraCT register, the frequency of AEs, the frequency of non-serious AEs with an incidence of greater than 5 % (in preferred terms) and the frequency of SAEs will be summarized.

For support of lay summaries, the frequency of subjects with drug-related SAEs will be summarized by treatment, primary SOC and preferred term.

All AEs occurring in screening, on-treatment and follow-up phase will be listed.

